**On-treatment virologic response:**

Virologic response is quantitative HCV RNA concentration  $<$ LLOQ at any timepoint post-first dose of study drug. An SVR is HCV RNA  $<$ LLOQ at Weeks 4, 8, 12, 18 or 24 after cessation of study treatment.

Time to virologic response is defined as the number of days since the first day of medication intake until the first day that the threshold was achieved. The following thresholds are considered:

- HCV RNA Not Detected
- HCV RNA Not Detected or HCV RNA  $<$ LLOQ Detected

### 9.3.2 Analysis Methods

The efficacy analysis will be performed on the Safety set and Per Protocol set, by cohort.

Descriptive statistics per cohort and per time point for the continuous parameter (actual values and changes from baseline in  $\log_{10}$  IU/mL HCV RNA) will be calculated.

Tabulations (numbers and proportions) per cohort and per time point for the categorical parameters will be provided. The observed proportion of subjects with SVR4 and SVR24 will be analyzed in the same way as the primary endpoint.

The influence of early virologic response parameters on SVR12 will be explored.

In addition, the reason for failure will be explored by type of failure (see definition of failure above). If more than one type of failure occurs, the order as presented below should be respected:

- a) viral relapse
- b) viral breakthrough
- c) confirmed detected at EOT
- d) missing at time point of SVR

Graphs of individual subject values (spaghetti plots) will be generated for each cohort for the viral load (VL) over time.

Graphs for mean VL change from baseline (+/- SD) over time will be generated for each cohort.

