**Otherwise SVR12 is classified as a failure (0).**

\* Confirmed means that the criterion should be fulfilled at 2 or more consecutive time points or at the last observed time point.

Time point of SVR12:

- 12 weeks after the actual EOT (i.e. the last available measurement in the SVR12 analysis window)
- or, if not available, the first available measurement at least 12 weeks after the actual EOT (i.e. the first available measurement after the SVR12 analysis window)
- or, if not available (i.e. no measurement at least 12 weeks after the actual EOT), the subject is considered a failure.

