#### 9.3.1 Definitions

**SVR4, SVR18 and SVR24** are defined similarly as SVR12 but with 4 weeks, 18 weeks and 24 weeks respectively, instead of 12 weeks.

In addition, for SVR24, the time point of SVR is defined as follows:

- 24 weeks after actual EOT (i.e. the last available measurement in follow up Week 24 analysis window)
- or, if not available, the first measurement available, after the follow-up Week 24 analysis window
- or, if not available, the last measurement available in the SVR18 analysis window, on condition that the time point of SVR24 has been reached

- or, if not available, the last measurement available in the follow up Week 12 analysis window (on condition that the time point of SVR24 has been reached)
- or, if not available, the subject is considered as not having SVR24

For SVR18, the timepoint of SVR is defined as follows:

- 18 weeks after the actual EOT (i.e. the last available measurement in follow up Week 18 analysis window)
- or, if not available, the subject is considered as not having SVR18

**On-Treatment failure** is defined as subjects who did not achieve SVR12 and with confirmed HCV RNA  $\geq$ LLOQ at the actual end of study drug treatment. Includes subjects:

- With viral breakthrough, defined as a confirmed increase of  $>1$  log10 in HCV RNA from nadir, or confirmed HCV RNA of  $>100$  IU/mL in subjects whose HCV RNA had previously been  $<$ LLOQ while on treatment.
- With inadequate virologic response, defined as  $<1$  log10 decline from baseline in HCV RNA after 4 weeks of treatment
- Who do not experience viral breakthrough or inadequate virologic response and have confirmed HCV RNA  $\geq$ LLOQ at the actual end of study drug treatment (e.g., completed study drug treatment, discontinued due to adverse events, withdrawal of consent).

**Viral Relapse** is defined as follows:

Subjects who achieved HCV RNA  $<$ LLOQ at the actual end of study drug treatment and developed HCV RNA  $\geq$ LLOQ during post-treatment follow up.

**Failure (No SVR12):** Subjects who did not achieve SVR12, including:

- On-treatment failure (see above)
- Post-treatment failure, including subjects with:
  - Viral relapse (see above)
  - Missing HCV RNA at time point of SVR12

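### In SAP 9.3.2, item c (detected at EOT) conflicts with the ≥LLOQ definition in 9.3.1, so some subjects with no SVR12 sample are filed under the wrong failure type; separately, inadequate response has no row

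*SAP*

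**What the plan says.** SAP 9.3.1 (and, in the same terms, the protocol's Definitions and section 8.2.2) defines on-treatment failure as no SVR12 together with confirmed HCV RNA ≥LLOQ "at the actual end of study drug treatment. Includes subjects". Three sub-types follow: viral breakthrough; inadequate virologic response (less than a 1 log10 decline after 4 weeks); and a residual group, described as those "Who do not experience viral breakthrough or inadequate virologic response and have confirmed HCV RNA" ≥LLOQ at actual end of treatment. Post-treatment failure covers viral relapse and "Missing HCV RNA at time point of SVR12".

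SAP 9.3.2 then says that "the reason for failure will be explored by type of failure (see definition of failure above"), and adds: "If more than one type of failure occurs, the order as presented below should be respected". The order is a) viral relapse, b) viral breakthrough, then "c) confirmed detected at EOT", then "d) missing at time point of SVR".

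The footnote to the SVR12 algorithm in SAP 9.2.1 states: "Confirmed means that the criterion should be fulfilled at 2 or more consecutive time points or at the last observed time point".

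**The concern.** The ranked list does not match the definitions it is meant to summarise, in two ways.

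- **Threshold.** Item c asks only whether virus was detected. The definition asks whether it was quantifiable. Because c outranks d, a subject with low-level detectable RNA at EOT who is later lost can be filed as detectable at EOT instead of as missing.
- **Missing category.** Inadequate virologic response is a defined sub-type in 9.3.1, a reason for permanent treatment discontinuation (protocol 4.6.1) and part of a futility criterion (protocol 4.8.1). It has no line in the list.

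What is at stake is how a cohort's failures are read. Lack of suppression on drug and loss to follow-up mean different things for a regimen, and in cohorts of 10 to 20 each failure is conspicuous.

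**Working it through.** The list carries no numerical claim, so there is no figure of the plan to reproduce. The check is to classify each pattern of SVR12 failure twice: by the literal order in 9.3.2, and by the definitions in 9.3.1.

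**Inputs**

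1. Result states (SAP 9.2.1, 9.3, 9.3.1): not detected; <LLOQ detected; ≥LLOQ. LLOQ and LOD are both 15 IU/mL, but the first two states are kept apart and imputed as 13 and 14 IU/mL (SAP 9.1.2). Detected therefore means the second or third state. Virologic response means the first or second. The overlap is <LLOQ detected.
2. Confirmed (SAP 9.2.1): met at two or more consecutive time points, or at the last observed one.
3. No HCV RNA result at or after the SVR12 time point is an SVR12 failure (SAP 9.2.1).
4. Rule: the first match in the order a, b, c, d.

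**Classification of SVR12 failures**

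| EOT result | Other feature | Follow-up | 9.3.2 as written | 9.3.1 |
|---|---|---|---|---|
| Not detected | – | SVR12 missing, no relapse | d, missing | missing |
| <LLOQ detected, confirmed | – | SVR12 missing, no relapse | **c** | **missing** |
| <LLOQ detected, not confirmed | – | SVR12 missing, no relapse | d, missing | missing |
| Not detected or <LLOQ detected | – | ≥LLOQ | a, relapse | relapse |
| ≥LLOQ, confirmed | breakthrough | any | b | breakthrough |
| ≥LLOQ, confirmed | inadequate response | any | **c** | **inadequate response** |
| ≥LLOQ, confirmed | neither | any | c | residual ≥LLOQ group |

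The two rules disagree in two rows only.

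**When the second row arises.** Confirmation holds if the EOT sample is the subject's last. It also holds if two consecutive visits were <LLOQ detected, for example Weeks 7 and 8 of an 8-week cohort. In that case a suppressed early follow-up sample does not rescue the subject from c.

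**Where inadequate responders go.** The lowest screening viral load allowed is 10^4 IU/mL (protocol 4.2, cirrhosis cohorts). Taking that as baseline, a decline of less than 1 log10 leaves more than 10,000 / 10 = 1,000 IU/mL, far above 15. With treatment stopped on that finding, these subjects are ≥LLOQ at EOT and fall into c. They are merged with the residual ≥LLOQ group, not filed as missing.

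**Size per subject**, with all cohort subjects as denominator: 1/20 = 5.0 points; 1/10 = 10.0 points. In the first disagreement, row c gains that amount and row d loses it.

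**What does not move.** Both patterns are SVR12 failures under either rule, so the SVR12 count and its Clopper-Pearson interval are unchanged.

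**The case against.** The strongest defence is that the sentence introducing the list points back to the definition of failure, so item c is naturally read as shorthand for the residual ≥LLOQ sub-type. It may well have been meant that way. But the definitions referred to contain no detected category and do contain inadequate response. The cross-reference exposes the mismatch and leaves the programmer to choose.

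It is also fair to say that this breakdown is exploratory, that inadequate responders remain on-treatment failures under 9.3.1, and that their data are visible elsewhere: an adverse-event listing for subjects with <1 log decline (14.3.2.4), an HCV RNA listing for virologic failures (16.2.6.2) and individual viral-load plots (14.4.5.1). That stands, and it limits the point.

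Three stronger readings are tempting, and the documents do not support them.

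- **Any suppressed subject who is lost is misfiled.** No. A subject not detected at EOT goes to d under both rules. The omission of inadequate response plays no part in this misfiling.
- **The secondary endpoint of on-treatment failure shifts.** It has its own definition in 9.3.1, and the ranked list does not redefine it. The residual risk is practical: Appendix 3 lists one failure table (14.4.4) and no separate table for on-treatment failure. The SAP does not say that 14.4.4 is built from the ranked list.
- **Several subjects would be affected, multiplying the on-treatment failures seen so far.** In Cohorts 1, 1b, 2 and 3, 20 + 18 + 20 + 20 = 78 of 80 reached SVR24 and the other two relapsed (protocol 1.2.1.2), so 0 of 80 failed for a missing sample. The exact two-sided 95% upper limit is 1 − 0.025^(1/80) = 4.5%. The share <LLOQ detected at EOT is not given. Nor is there a firm base count: the available text gives no failure type for the 5 Cohort 5 (8-week), 1 Cohort 4 (12-week) and 1 Cohort 6 subjects without SVR.

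**Conclusion.** The list in SAP 9.3.2 is wrong as written. Item c uses a looser threshold than the SAP and protocol definition and outranks the missing category, so one specific pattern is misclassified: confirmed <LLOQ detected at EOT, no relapse and no SVR12 sample. As a separate defect, inadequate virologic response is merged into c.

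The consequence is confined to the failure-type breakdown. The per-subject shift above assumes percentages of all subjects in the cohort. No expected number of misfiled subjects can be given from the documents, and the cohorts with SVR24 results suggest that missing SVR12 samples are uncommon. The conclusion that the on-treatment failure proportion is unaffected rests on its being programmed from 9.3.1. The correction is worth making because it brings a stated rule into line with the plan's own definitions.

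**What to change.** Replace the ranked list in SAP 9.3.2 with:

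a) viral relapse;
b) viral breakthrough;
c) inadequate virologic response;
d) confirmed HCV RNA ≥LLOQ at actual EOT, without b or c;
e) missing HCV RNA at the SVR12 time point.

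State that <LLOQ detected at EOT does not qualify for d. It would also help to say that the on-treatment failure and relapse proportions come from the 9.3.1 definitions, and where in the output list they appear.

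The cost is a change of SAP wording and one derivation. No new data, visits or samples are needed.

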## 10. Reporting conventions

All tables, figures and listings are detailed in section [12.3](#). They will be prepared using SAS® software as rtf files and the rtf files will be compiled as Word files (one Word file by main section).

The footers will be presented as follows: --- STUDY <study protocol code> / <name of the program>.SAS / <name of the output>.RTF / DDMMYY HH:MM ---.

Table and Listing Page Set Up Requirements:

- Font Type = Courier New
- Font Size = 8 pt (at a minimum)
- Page Margins: Top=2 cm; Bottom=2 cm; Left=2 cm; Right=2 cm
- Paper Size = A4 (21 cm x 29.7 cm)
- Page Orientation: Landscape
- Graphs: Portable Network Graphics (PNG) format

Summary statistics will be presented as follows.

Parameter (unit)	Statistics / Category	Group X (N=xx)
Quantitative variable*	n	xx
	Mean ± SD	xx.xx ± xx.xx
	SEM	xx.xx
	Median	xx.xx
	Min ; Max	xx.x ; xx.x
Qualitative variable	Class 1 (n,%)	xx ( xx.x)
	Class 2 (n,%)	xx ( xx.x)
	...	...

\* For demographics and Baseline characteristics and for Safety summary tables:

All statistics, except the minimum and the maximum, will be provided with an additional decimal compared to the variable itself.

For PK summary tables:

- if n=1 or n=2, do not display other statistics than n
- For tmax, only minimum, median, maximum and number of observations will be reported.
- For calculated values, PK parameters and descriptive statistics up to, but not including 100, display to 3 significant figures, for example:
  - 0.35769 is reported 0.358
  - 3.5769 is reported 3.58
  - 35.769 is reported 35.8
  - 357.69 is reported 358
  - For values ≥ 1000, the whole integer is reported (example 3576.9 is reported as 3577)

tmax and tlag values are to be reported to 2 decimal places; half-life is to be reported to 1 decimal place.

Coefficient of Variation is reported to 1 decimal place.

Ratios and confidence interval are reported to 2 decimal places.

Drug concentration data that could not be obtained will be listed as NS (No Sample) in data tabulations.

## 11. Appendices

### 11.1 Appendix 1 - Schedule of assessments of the study

**Table 6-1. Schedule of Events for 8 or 12\*-Week Treatment Groups**

Assessments	Interval	Day			Week**							
	Screen -50 to -1	1	2	3	1	2	3	4	5	6	7	8
AL-335 / ODV-SMV 		←----->										
Obtain informed consent before study procedures	X											
Demographics	X											
Height, Weight, BMI 	X											X 
Drug Screen	X											
Medical History	X											
Echocardiogram	X (-3 days)							X (+3 days)				X (+3 days)
Triplicate 12-Lead electrocardiogram	X	X			X	X	X	X	X	X	X	X
Physical Exam and vital signs 	X	X			X	X	X	X	X	X	X	X
Hepatitis and HIV screen (HBsAg, HBsAb, HBeAb, HCVAb, HIVAb)	X											
Alpha-fetoprotein, glycosylated HbA1C	X											
Liver Ultrasound (subjects with cirrhosis, if results from within the past 6 months are not available)	X											
HCV genotype	X											
IL28B genotype		X										
Randomization		X										
AE & Conmed Evaluation	X	X	X	X	X	X	X	X	X	X	X	X

 Cohorts 1b, 2 to 16 may or may not include SMV. Dosing frequency will be qd except possibly for ODV which may also be dosed qod.

 Weight only collected at last treatment visit.

 Complete Physical Exams, including vital signs (BP, HR, RR, body temperature), are to be done at screening, predose on Day 1, early termination, safety follow-up visits. Symptom directed physical exams and vitals are to be collected as necessary at all other visits.

 Randomization may take place up to 4 days before first dose.

**Table 6-1. Schedule of Events for 8 or 12\*-Week Treatment Groups**

Assessments	Interval	Day			Week**								
		Screen -50 to -1	1	2	3	1	2	3	4	5	6	7	8
PK Samples 			X				X	X	X		X		X
Hematology 		X	X			X	X		X		X		X
Serum Chemistries 		X	X			X	X		X		X		X
Urinalysis		X	X			X	X		X		X		X
ALT/AST 		X	X			X	X	X	X	X	X	X	X
HCV RNA concentrations 		X	X	X	X	X	X	X	X	X	X	X	X
Plasma for drug resistance monitoring 			X	X	X	X	X	X	X	X	X	X	X
Pregnancy Test 		X							X				X
Stored serum sample 		X	X			X	X	X	X	X	X	X	X

 A single predose PK sample will be collected at each indicated visit for AL-335 (and metabolites), ODV and SMV concentrations for all subjects. In addition, PK samples will be collected at Weeks 3 and 6, 2-4 hours postdose, and at Weeks 4 and 8, 6-8 hours postdose. Subjects in the intensive PK subset will have the following samples collected at the Week 2 visit Predose (within 0.5 hour) and 0.5, 1, 2, 3, 4, 6, 9, 12, and 24 hours postdose.

 Blood for routine safety evaluations should be collected in a fasted state.

 Plasma for HCV RNA analysis to be collected predose at Day 1.

 Plasma collected for HCV RNA resistance monitoring will be collected at the same time as HCV RNA quantification. The Day 1 samples must be collected predose.

 Heterosexually active women of childbearing potential. A highly sensitive pregnancy test (e.g., urine or plasma) must be conducted immediately (within 4 days) prior to initiating treatment on Day 1 (local results may be used for this eligibility determination)

 For additional safety investigations as needed.

\* If a 12-week regimen is evaluated, the Week 5, 6, 7, and 8 visits will be repeated at Weeks 9, 10, 11, and 12, respectively.

\*\* Weekly visit may occur  $\pm 1$  day from the expected visit date.

**Table 6-2. Schedule of Events for a 6-Week Treatment Group**

Assessments	Interval	Day			Week*						
	Screen -50 to -1	1	2	3	1	2	3	4	5	6	
AL-335+ODV±SMV 		<----->									
Obtain informed consent before study procedures	X										
Demographics	X										
Height, Weight, BMI 	X									X 	
Drug Screen	X										
Medical History	X										
Echocardiogram	X (±3 days)							X (±3 days)		X (±3 days)	
Triplicate 12-Lead electrocardiogram	X	X			X	X	X	X	X	X	
Physical Exam and vital signs 	X	X			X	X	X	X	X	X	
Hepatitis and HIV screen (HBsAg, HBsAb, HBcAb, HCVAb, HIVAb)	X										
Alpha-fetoprotein, glycosylated HbA1C	X										
Liver Ultrasound (subjects with cirrhosis, if results from within the past 6 months are not available)	X										
HCV genotype	X										
IL28B genotype		X									
Randomization		X									
AE & Conmed Evaluation	X	X	X	X	X	X	X	X	X	X	

 Cohorts 1b, 2 to 16 may or may not include SMV. Dosing frequency will be qd except possibly for ODV which may also be dosed qod.

 Weight only collected at Week 6.

 Complete Physical Exams, including vital signs (BP, HR, RR, body temperature), are to be done at screening, predose on Day 1, early termination, safety follow-up visits. Symptom directed physical exams and vitals are to be collected as necessary at all other visits.

 Randomization may take place up to 4 days before first dose.

**Table 6-2. Schedule of Events for a 6-Week Treatment Group**

Assessments	Interval	Day			Week*					
	Screen -50 to -1	1	2	3	1	2	3	4	5	6
PK Samples 		X				X	X	X		X
Hematology 	X	X			X	X		X		X
Serum Chemistries 	X	X			X	X		X		X
Urinalysis	X	X			X	X		X		X
ALT/AST 	X	X			X	X	X	X	X	X
HCV RNA concentrations 	X	X	X	X	X	X	X	X	X	X
Plasma for drug resistance monitoring 		X	X	X	X	X	X	X	X	X
Pregnancy Test 	X							X		
Stored serum sample 	X	X			X	X	X	X	X	X

 A single predose PK sample will be collected at each indicated visit for AL-335(and metabolites), ODV and SMV concentrations for all subjects. In addition, PK samples will be collected at Weeks 3 and 6, 2-4 hours postdose, and at Week 4, 6-8 hours postdose. Subjects in the intensive PK subset will have the following samples collected at the Week 2 visit Predose (within 0.5 hour) and 0.5, 1, 2, 3, 4, 6, 9, 12, and 24 hours postdose.

 Blood for routine safety evaluations should be collected in a fasted state.

 Plasma for HCV RNA analysis to be collected predose at Day 1.

 Plasma collected for HCV RNA resistance monitoring will be collected at the same time as HCV RNA quantification. The Day 1 samples must be collected predose.

 A highly sensitive pregnancy test (e.g., urine or plasma) must be conducted immediately (within 4 days) prior to initiating treatment on Day 1 (local results may be used for this eligibility determination)

 For additional safety investigations as needed.

\* Weekly visit may occur  $\pm 1$  day from the expected visit date.

**Table 6-3. Schedule of Events for a 4-Week Treatment Group**

Assessments	Interval	Screen -50 to -1	Day 1	Day 2	Day 3	Week 1*	Week 2*	Week 3*	Week 4*
AL-335+ODV±SMV 			<----->						
Obtain informed consent before study procedures		X							
Demographics		X							
Height, Weight, BMI 		X							X 
Drug Screen		X							
Medical History		X							
Echocardiogram		X (+3 days)							X (+3 days)
Triplicate 12-Lead electrocardiogram		X	X			X	X	X	X
Physical Exam and vital signs 		X	X			X	X	X	X
Hepatitis and HIV screen (HBsAg, HBsAb, HBcAb, HCVAb, HIVAb)		X							
Alpha-fetoprotein, glycosylated HbA1C		X							
Liver Ultrasound (subjects with cirrhosis, if results from within the past 6 months are not available)		X							
HCV genotype/subtype		X							
IL28B genotype			X						
Randomization 			X						
AE & Conmed Evaluation		X	X	X	X	X	X	X	X

 Cohorts 1b, 2 to 16 may or may not include SMV. Dosing frequency will be qd except possibly for ODV which may also be dosed qod.

 Weight only collected at Week 4.

 Complete Physical Exams, including vital signs (BP, HR, RR, body temperature), are to be done at screening, predose on Day 1, early termination, safety follow-up visits. Symptom directed physical exams and vitals are to be collected as necessary at all other visits. Vital signs will be collected at all visits indicated.

 Randomization may take place up to 4 days before first dose.

**Table 6-3. Schedule of Events for a 4-Week Treatment Group**

Assessments	Interval	Screen -50 to -1	Day 1	Day 2	Day 3	Week 1*	Week 2*	Week 3*	Week 4*
PK Samples 			X			X	X	X	X
Hematology 		X	X			X	X		X
Serum Chemistries 		X	X			X	X		X
Urinalysis		X	X			X	X		X
ALT/AST 		X	X			X	X	X	X
HCV RNA concentrations 		X	X	X	X	X	X	X	X
Plasma for drug resistance monitoring 			X	X	X	X	X	X	X
Pregnancy Test 		X							X
Stored serum sample 		X	X			X	X	X	X

 A single predose PK sample will be collected at each indicated visit for AL-335 (and metabolites), ODV and SMV concentrations for all subjects. In addition, PK samples will be collected at Week 3, 2-4 hours postdose, and at Week 4, 6-8 hours postdose. Subjects in the intensive PK subset will have the following samples collected at the Week 2 visit Predose (within 0.5 hour) and 0.5, 1, 2, 3, 4, 6, 9, 12, and 24 hours postdose.

 Blood for routine safety evaluations should be collected in a fasted state.

 Plasma for HCV RNA analysis to be collected predose at Day 1, 2 and 3.

 Plasma collected for HCV RNA resistance monitoring will be collected at the same time as HCV RNA quantification. The Day 1 samples must be collected predose.

 A highly sensitive pregnancy test (e.g., urine or plasma) must be conducted immediately (within 4 days) prior to initiating treatment on Day 1 (local results may be used for this eligibility determination)

 For additional safety investigations as needed.

\* Weekly visit may occur  $\pm 1$  day from the expected visit date.

**Table 6-4. Schedule of Events for Post-dosing (Safety and Virology) Follow-up Visits (All Treatment Cohorts)**

Post-dosing Follow-up							
Assessment	Early Termination (ET) Visit 	Safety Follow-up Visit 4 Weeks (±1 week) After the Last Actual Dose of Study Drug	Virology Follow-up Visits (After end of Treatment  OR After Time of Treatment Failure [if earlier]) 				Week 24 (±2 weeks)
			Week 4 (±1 week) 	Week 8 (±1 weeks)	Week 12 (±2 weeks)	Week 18 (±2 weeks)	
Physical Exam 	X	X					
Echocardiogram	X	X					
Vital Signs	X	X					
Triplicate 12 Lead ECG	X	X					
Serum Chemistry w/ ALT & AST	X	X					
Hematology	X	X					
Urinalysis	X	X					
HCV RNA concentration	X	X	X	X	X	X	X
Plasma for drug resistance monitoring	X	X	X	X	X	X	X
AE & Conmed Evaluation	X	X	X	X	X	X	X
PK Samples 	X	X	X	X	X	X	X
Pregnancy test 	X	X		X	X		X
Stored Serum Sample 	X	X					

 Subjects who prematurely discontinue from their assigned study treatment should return to the clinic as soon as possible for an Early Termination Visit. If the timing of the Early Termination Visit coincides with the Safety Follow up Visit, then assessments for the Early Termination Visit should be conducted.

 For subjects with less than lower limit of quantitation (<LLOQ) HCV RNA at actual end of treatment (EOT) (if prematurely discontinued treatment, discontinuation was for reasons other than on-treatment virologic failure (e.g., AE).

 On-treatment failure is defined as virologic failure or breakthrough. No subject will be followed for more than 24 weeks.

 Note: The Week 4 Virology Follow up Visit will coincide with the Safety Follow-up Visit for most subjects and may be replaced by the Safety Follow-up Visit in these cases; it will not coincide for subjects who have relapse or for subjects who discontinue early with <LLOQ HCV RNA.

 Complete Physical Exams, including vital signs (BP, HR, RR, body temperature), are to be done at screening, predose on Day 1, early termination, safety follow-up visits. Symptom directed physical exams and vitals are to be collected as necessary at all other visits.

 PK sampling will be conducted for ODV at the time of visit.

 Heterosexually active women of childbearing potential.

 For additional safety investigations as needed.

